## 7. Study Subjects and Demographics

### 7.1. Disposition of Subjects and Withdrawals

Disposition will include tabulations of the number of subjects who received treatment, reasons for discontinuation from the study, and number of subjects in each analysis population. This summary will be based on all subjects enrolled.

All disposition information will be included in a listing.

### 7.2. Protocol Violations and Deviations

Protocol deviations will be listed.

### 7.3. Demographics and Other Baseline Characteristics

Summary statistics for age, gender, race, ethnicity, height, weight, Commercially Confidential Information will be presented.

Medical history will be listed, and the number and percentage of subjects reporting various medical histories grouped by MedDRA System Organ Class (SOC) and Preferred Term (PT) will be tabulated.

Time since first ET symptom, time since ET diagnosis, treatment type, trigger type, and frequency of triggers will be summarized descriptively. The number of subjects who report that alcohol reduces tremor severity and the number of subjects with a first or second-degree blood relative with ET will also be summarized.

Disease history, including prior treatments for ET, ET triggers, and family history of ET, will also be listed.

These analyses will be conducted for the Safety population.

### 7.4. Exposure and Compliance

All subjects were expected to receive treatment twice daily for 14 consecutive days for a total of 28 doses. Total number of doses taken, number of missed doses, and compliance (%) will be summarized and listed for the Safety Population. Compliance via capsule count is defined in Section 6.1.8 as the rate of actual number of doses taken compared to the intended number of doses taken during the 2-week treatment period. Treatment compliance (rounded to the whole number) will also be categorized as <70%, ≥70 to 79%, ≥80 to 89%, ≥90% to 100%, and >100%.

Commercially Confidential Information

## 8. Efficacy Analysis

All efficacy data (including change from baseline) will be summarized and presented in tabular format and in data listings.

Efficacy variables include TETRAS-PS score, TETRAS-PS upper limb subscale score, TETRAS-PS upper limb tremor item 4 total score, Kinesia Upper Limb Tremor score,

Commercially Confidential Information

Analyses of these data will be conducted on both the FAS and Per-Protocol Population within the same output for tables; figures will only be presented on the FAS.

### **8.1. Primary Efficacy Analysis**

Not applicable. The primary analysis for this study is safety.

### **8.2. Secondary Efficacy Analysis**

Normality assumptions of efficacy endpoints will be tested using the Anderson-Darling method. If the  $P$  value for the normality test is  $>0.05$  the data will be considered normally distributed and will be analyzed as specified in subsequent sections. Otherwise, if the  $P$  value is  $\leq 0.05$  the data will be considered non-normal and the Wilcoxon signed rank test will be used to assess the within-subject changes. The estimates, CIs and  $P$  values will be displayed.

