### **11.2.4 Sample Size Determination**

Approximately 30 subjects will be enrolled. No formal statistical power analysis was conducted. Each subject will be assessed for change from their own Baseline.

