#### **3.2. Sample Size and Power**

Up to 30 subjects will be enrolled. No formal statistical power analysis was conducted.

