## 4. Statistical Analysis and Reporting

### 4.1. Introduction

Data processing, tabulation of descriptive statistics, calculation of inferential statistics, and graphical representations will be performed primarily using SAS (release 9.4 or higher).

Commercially Confidential Information If the use of other software is warranted, the final statistical methodology report will detail what software was used for what purposes.

Continuous (quantitative) variable summaries will include the number of subjects (n) with non-missing values, mean, standard deviation (SD), median, minimum, and maximum.

Categorical (qualitative) variable summaries will include the frequency and percentage of subjects who are in the particular category for each possible value. In general, the denominator for the percentage calculation will be based upon the total number of subjects in the study population, unless otherwise specified. The denominator for by-visit displays will be the number of subjects in the relevant study population with non-missing data at each visit. If there is any missing value for a categorical analysis, a “Missing” category will be displayed as the last category in the table for the variable.

For weight, height, CCI one decimal place will be used for all summary statistics. For all other summaries, the minimum and maximum will be reported with the same degree of precision (i.e., the same number of decimal places) as the observed data. Measures of location (mean and median) and confidence interval boundaries will be reported to 1 degree of precision more than the observed data, up to 3 decimal places. Measures of spread (SD) will be reported to 2 degrees of precision more than the observed data, up to 3 decimal places.

Percentages will be presented to 1 decimal place, unless otherwise specified. Percentages equaling 0 or 100 will be displayed with no decimal places or percentage symbols.

Fractional numeric values will be presented with a zero to the left of the decimal point (for example, 0.12 – 0.30).

Unless otherwise indicated, all statistical tests will be conducted at the 0.05 significance level using 2-tailed tests, and *P* values will be reported. Corresponding 95% confidence intervals (CIs) will be presented for statistical tests, where applicable.

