#### 6.1.2. Categorization of Subjects

All subjects will be categorized into the following 2 groups based on under which protocol amendment they were enrolled:

- Cohort-1: Subjects enrolled under Protocol Amendment 1.0
- Cohort-2: Subjects enrolled under Protocol Amendment 2.0 or 3.0

All analyses will be presented overall and by cohort.

Commercially Confidential Information

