#### **8.2.1. TETRAS Performance Subscale Scores**

The TETRAS-PS Subscale (Version 3.1) score includes the following 9 items: head tremor, face (including jaw) tremor, voice tremor, upper limb tremor (left/right), lower limb tremor, Archimedes spirals, handwriting, dot approximation task, and standing tremor. Scores for each item range from 0 to 4 in increments of 0.5. Derivation for the TETRAS-PS Total score is described in Section 6.1.8. For lower limb tremor, only the maximum of the item 5 scores will be used. The TETRAS-PS assessments will be administered by a certified rater (referred to as a local rater hereafter) at Screening, Pre-dose, Day 1, Day 7, Day 14, and Day 21. The TETRAS-PS assessments will also be recorded using videography for centralized evaluation and rating by independent blinded central raters (neurologists) with expertise in the assessment of ET. All scores (item scores and total scores) by both local and central raters will be analyzed in the same way as described below for central rater data.

Observed values and change from baseline in each item score and in TETRAS-PS total score by central rater will be summarized overall, by cohort (see Section 6.1.2), and by study visit using descriptive statistics.

Additionally, tests of hypotheses comparing mean and median TETRAS-PS total scores between baseline and subsequent study visits will be conducted using a 2-sided paired t-test or Wilcoxon signed rank test. The null hypothesis is that the change from baseline in TETRAS-PS total score to subsequent visit is 0 with a 2-sided alternative considering a difference not 0 (significant changes in tremor).

As a supportive analysis, change from Screening to Baseline and change from Day 14 to Day 21 in each item score and in TETRAS-PS total score will be summarized overall and by cohort (see Section 6.1.2) using descriptive statistics.

Commercially Confidential Information

Commercially Confidential Information

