### **8.2.2. TETRAS Upper Limb Subscale Score**

Upper limb tremor is assessed during the following maneuvers: forward outstretched posture, lateral “wing beating” posture, kinetic (finger-chin-finger) testing, Archimedes spirals, handwriting, and dot approximation task. Each side of the body (right and left) is assessed and scored individually for all maneuvers except handwriting. The individual item question scores for each side of the body range from 0 to 4, with higher scores indicating more tremors. Derivation for the upper limb subscale score is described in Section [6.1.8](#).

Assessments will be administered at Screening, Pre-dose, Day 1, Day 7, Day 14, and Day 21. Assessment results (scores) by local and central rater will be analyzed in the same way as described below for central rater score data. Observed values and change from baseline to all subsequent study visits in the upper limb subscale score will be summarized overall, by cohort (see Section [6.1.2](#)), and by study visit using descriptive statistics.

Additionally, tests of hypotheses comparing mean and median TETRAS-PS upper limb subscale scores between baseline and subsequent study visits will be conducted using a 2-sided paired t-test and a Wilcoxon signed rank test, respectively. The null hypothesis is that the change from baseline in TETRAS-PS upper limb subscale score to subsequent visit is 0 with a 2-sided alternative considering a difference in either direction (i.e., change from baseline not equal to 0, representing significant change in tremor).

As a supportive analysis, change from Screening to Baseline and change from Day 14 to Day 21 in each item score and in TETRAS-PS upper limb subscale score will be summarized overall and by cohort (see Section [6.1.2](#)) using descriptive statistics.

Commercially Confidential Information

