Screening						
n	XX	XX	XX	XX	XX	XX
Mean (SD)	XX.X (XX.XX)					
Median	XX.X	XX.X	XX.X	XX.X	XX.X	XX.X
Min, Max	XX, XX					
Baseline [1]						
n	XX	XX	XX	XX	XX	XX
Mean (SD)	XX.X (XX.XX)					
Median	XX.X	XX.X	XX.X	XX.X	XX.X	XX.X
Min, Max	XX, XX					
Change from Screening						
n	XX	XX	XX	XX	XX	XX
Mean (SD)	XX.X (XX.XX)					
Median	XX.X	XX.X	XX.X	XX.X	XX.X	XX.X
Min, Max	XX, XX					
Mean Change from Screening (SE) [2] (95% CI for Mean Change from Screening)	XX.X (X.XX) (XX.X, XX.X)					
P value for Mean Change from Screening [3]	X.XXX	X.XXX	X.XXX	X.XXX	X.XXX	X.XXX
P value for Median Change from Screening [4]	X.XXX	X.XXX	X.XXX	X.XXX	X.XXX	X.XXX

Abbreviations: CI = confidence interval; TETRAS-PS = Tremor Research Group Essential Tremor Rating Assessment Scale (TETRAS)-performance subscale (PS); SE = standard error.

Note: TETRAS-PS Total score is derived as the sum of all of the individual item scores, with the exception of item 5, only the maximum of the lower limb tremor scores will be counted. Each individual item question score ranges from 0 to 4, where higher scores indicate worse performance. A negative change indicates improvement.

[1] The baseline value is the last observation recorded prior to the first dose of treatment.

[2] Estimates for mean change from screening/baseline and accompanying 95% CIs and P values are from a paired t-test

[3] P-value for testing mean change from screening/baseline is based on a paired t-test with null hypothesis that the change in TETRAS-PS total score to subsequent visit is 0 with a 2-sided alternative considering a difference not equal to 0 (change in tremor).

[4] P-value for testing median change from screening/baseline is based on a Wilcoxon signed-rank test with null hypothesis that the change in TETRAS-PS total score to subsequent visit is 0 with a 2-sided alternative considering a difference not equal to 0 (change in tremor).

SOURCE: Listing 16.2.6.1.1

Table 14.2.1.1.1 (cont.)

Summary of Central Rater TETRAS-PS Scores by Study Visit  
FAS and Per-Protocol Population

Parameter: TETRAS-PS Total Score

Study Visit Statistic	Full Analysis Set			Per-Protocol Population		
	Cohort-1 (N=XX)	Cohort-2 (N=XX)	Overall (N=XX)	Cohort-1 (N=XX)	Cohort-2 (N=XX)	Overall (N=XX)
% Change from Screening						
n	XX	XX	XX	XX	XX	XX
Mean (SD)	XX.X (XX.XX)	XX.X (XX.XX)	XX.X (XX.XX)	XX.X (XX.XX)	XX.X (XX.XX)	XX.X (XX.XX)
Median	XX.X	XX.X	XX.X	XX.X	XX.X	XX.X
Min, Max	XX, XX	XX, XX	XX, XX	XX, XX	XX, XX	XX, XX

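### The SAP does not settle whether the t-test or the Wilcoxon P value is the TETRAS-PS result, and its normality switch adds type I error for the mean if changes are markedly skewed

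*SAP*

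**What the plan says.** SAP 8.2 tests the normality of the efficacy endpoints by Anderson-Darling with a cut-off of 0.05. Above the cut-off, the analysis follows the later subsections. At or below it, "the data will be considered non-normal and the Wilcoxon signed rank test will be used to assess the within-subject changes". The section promises estimates, CIs and P values without saying which estimate or interval goes with the Wilcoxon branch.

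The later subsections differ:

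- SAP 8.2.1 (TETRAS-PS total) frames hypotheses about mean and median together and says the tests "will be conducted using a 2-sided paired t-test or Wilcoxon signed rank test".
- SAP 8.2.2 (upper limb subscale) says they "will be conducted using a 2-sided paired t-test and a Wilcoxon signed rank test, respectively", so the mean gets the t-test and the median gets the Wilcoxon. SAP 8.2.3 (Item 4 total) says the same.
- The shell of Table 14.2.1.1.1 (SAP 14.2) has a t-test P value row and a signed-rank P value row in each change block. No row or footnote reports the normality result. Its footnote 2 takes the mean change and 95% CI from the paired t-test. The other TETRAS-PS score summaries reuse this shell.

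Protocol 11.2.2 describes the analysis as the mean change in score. SAP 4.1 says that, unless otherwise indicated, "all statistical tests will be conducted at the 0.05 significance level using 2-tailed tests". On size, SAP 3.2 says "Up to 30 subjects will be enrolled. No formal statistical power analysis was conducted", and SAP 6.1.2 adds "All analyses will be presented overall and by cohort".

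**The concern.** Two things are at stake. The first is which number counts. Two programmers could follow this SAP and headline different P values for the same score and visit, and a reader of the tables could not tell from the visible text which one the plan meant.

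The second is validity. The signed-rank test is a valid test of a zero mean or a zero median only if the changes are symmetric. Skewed changes break that symmetry and also make Anderson-Darling more likely to reject. With skewed data, therefore, the rule tends to choose the Wilcoxon test where it no longer tests the mean that the protocol targets.

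**Working it through.** **Which test governs**

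| Place | Test(s) | Normality condition? |
|---|---|---|
| SAP 8.2, P ≤ 0.05 | Wilcoxon | yes |
| SAP 8.2, P > 0.05 | as in later subsections | yes |
| SAP 8.2.1 | t-test *or* Wilcoxon | not restated |
| SAP 8.2.2, 8.2.3 | t-test *and* Wilcoxon | not restated |
| Table 14.2.1.1.1 shell | both P values; CI from t-test | none |

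Even the normal branch of 8.2 does not give one test for the subscale or Item 4, because 8.2.2 and 8.2.3 ask for two. A 95% t interval excludes 0 exactly when the two-sided t-test has P < 0.05. So whenever the Wilcoxon and t-test disagree at 0.05, the Wilcoxon P value contradicts the printed interval.

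How many cells are affected: 3 scores × 4 post-baseline visits × 3 columns (two cohorts and overall) × 2 populations × 2 raters = 144 cells, each with two P values. SAP 8.2 does not say whether scores or changes are pre-tested, or whether this is done cell by cell. If it is cell by cell and the data are normal, about 0.05 × 144 = 7.2 cells would switch by chance.

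**Type I error of the switch rule**

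The plan has no power figure to reproduce; its only stated figure is the 0.05 level.

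- From the documents: two-sided 0.05, Anderson-Darling cut-off 0.05, up to 30 subjects overall.
- Assumed, because the documents do not give them: cohort-like sizes of 10, 15 and 20, and the shape of the changes. Gamma shapes with parameter k have skewness 2/√k, so k = 16, 4, 1.78 and 1 give 0.5, 1, 1.5 and 2.
- Procedure: 40,000 simulated trials per case. Apply Anderson-Darling with estimated mean and SD, then the t-test if P > 0.05, otherwise the exact signed-rank test. Monte Carlo SE at 5% is √(0.05 × 0.95 / 40,000) ≈ 0.001.

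Check with normal changes, n = 30: t-test 4.9%, Wilcoxon 5.0%, switch rule 5.0%. The nominal level holds.

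True mean change 0, switch rule vs t-test alone:

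| Assumed skewness | n = 10 | n = 15 | n = 20 | n = 30 |
|---|---|---|---|---|
| 0.5 | 5.6 vs 5.6% | 5.4 vs 5.2% | 5.4 vs 5.2% | 5.4 vs 5.0% |
| 1 | 6.2 vs 6.3% | 6.5 vs 6.0% | 6.7 vs 5.8% | 7.3 vs 5.5% |
| 1.5 | 7.8 vs 8.1% | 8.5 vs 7.4% | 9.4 vs 7.0% | 10.9 vs 6.3% |
| 2 | 9.5 vs 10.1% | 10.9 vs 8.6% | 12.7 vs 8.1% | 16.0 vs 7.5% |

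At n = 30, Anderson-Darling rejects in 11.9%, 36.7%, 71.6% and 93.4% of these trials, so with strong skew the rule is almost the Wilcoxon test.

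Other results at n = 30:

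- Symmetric but non-normal changes (Laplace, t with 3 df): switch rule 5.1%.
- True median change 0, skewness 1, 1.5, 2: switch rule 9.6%, 12.6%, 14.9%; t-test 10.7%, 18.7%, 31.7%.
- True pseudo-median (the signed-rank test's own centre) 0, same skewness: switch rule 5.9% to 6.2%.
- The two tests disagree at 0.05 in 3.7%, 6.3% and 10.0% of trials at skewness 1, 1.5 and 2 (mean change 0), and in 2.7% with Laplace changes.

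**The case against.** The best defence is that nothing in the documents shows the changes to be skewed. The total is a change in a sum of 16 bounded item scores, a form that tends to average skewness out. If baseline and post-dose scores are exchangeable under the null, the changes are symmetric and the signed-rank test is valid.

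A reader might also infer that an Anderson-Darling rejection usually signals skewness. The documents do not support that. Items move in half-point steps, and discreteness and ties can trigger rejection by themselves. In simulated exchangeable item scores at n = 30 (assumed true mean 1.7, measurement SD 0.3 to 0.5, rounded to 0.5), the pre-test rejected for a single item in 82% to 100% of datasets while the switch rule stayed at 4.5% to 4.8%. For sums of 6, 11 and 16 scores it rejected in 6% to 22%, with the rule at 4.2% to 5.0%. This stands, and it confines the type I error point to marked skewness.

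The choice of target matters too. SAP 8.2.1 to 8.2.3 name mean and median. Judged against the median at n = 30, the rule does better than the t-test at skewness 1 or more. The protocol's mean target favours the t-test, but that is a condition of the argument.

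The shell rows are labelled mean and median with their tests named, so nothing is hidden. That is fair, but a label does not say which row is the result, and 8.2 implies that only one should be. SAP 6.1.4 on multiple comparisons and parts of 8.2.1 to 8.2.3 are redacted, so the statement that nothing settles the matter covers the visible text only.

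**Conclusion.** The inconsistency holds on the wording alone. SAP 8.2 and 8.2.1 point to a choice of test, 8.2.2 and 8.2.3 to two tests, and the shell prints both with one test's interval. No visible text ranks them.

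The type I error point holds conditionally: marked skewness, n of about 15 or more, and the mean as target. At n = 30 the excess over the t-test is 0.4 percentage points at skewness 0.5 (5.4 − 5.0), 1.8 at 1 (7.3 − 5.5), 4.6 at 1.5 (10.9 − 6.3) and 8.5 at 2 (16.0 − 7.5). There is none at n = 10 and no inflation for symmetric changes. These sizes rest on assumed gamma shapes.

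A reader might infer that this trial's efficacy P values carry a false-positive rate of 11% to 16%. The documents do not support that, because they give no distribution for the changes.

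Priority is low to moderate. These are secondary endpoints in an unpowered, open-label, single-arm study whose primary endpoint is safety, and no visible text makes success depend on a P value.

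**What to change.** - Delete the Anderson-Darling selection rule from SAP 8.2.
- Name the paired t-test, reported as mean change with 95% CI, as the analysis for each TETRAS-PS total and subscale score. This matches protocol 11.2.2.
- Keep the Wilcoxon signed-rank test as a labelled sensitivity analysis.
- Make SAP 8.2, 8.2.1, 8.2.2, 8.2.3 and the footnotes of the Table 14.2.1.1.1 shell say the same thing.

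The cost is SAP and footnote wording. The shells already hold both outputs, though the documents do not show whether anything has been programmed. There is a small statistical downside: the t-test is itself above 5% under strong skew (7.5% at skewness 2, n = 30; 10.1% at n = 10) and does not test the median. The retained Wilcoxon row lets a reader see when the two tests differ.

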#### **8.2.1. TETRAS Performance Subscale Scores**

The TETRAS-PS Subscale (Version 3.1) score includes the following 9 items: head tremor, face (including jaw) tremor, voice tremor, upper limb tremor (left/right), lower limb tremor, Archimedes spirals, handwriting, dot approximation task, and standing tremor. Scores for each item range from 0 to 4 in increments of 0.5. Derivation for the TETRAS-PS Total score is described in Section 6.1.8. For lower limb tremor, only the maximum of the item 5 scores will be used. The TETRAS-PS assessments will be administered by a certified rater (referred to as a local rater hereafter) at Screening, Pre-dose, Day 1, Day 7, Day 14, and Day 21. The TETRAS-PS assessments will also be recorded using videography for centralized evaluation and rating by independent blinded central raters (neurologists) with expertise in the assessment of ET. All scores (item scores and total scores) by both local and central raters will be analyzed in the same way as described below for central rater data.

Observed values and change from baseline in each item score and in TETRAS-PS total score by central rater will be summarized overall, by cohort (see Section 6.1.2), and by study visit using descriptive statistics.

Additionally, tests of hypotheses comparing mean and median TETRAS-PS total scores between baseline and subsequent study visits will be conducted using a 2-sided paired t-test or Wilcoxon signed rank test. The null hypothesis is that the change from baseline in TETRAS-PS total score to subsequent visit is 0 with a 2-sided alternative considering a difference not 0 (significant changes in tremor).

As a supportive analysis, change from Screening to Baseline and change from Day 14 to Day 21 in each item score and in TETRAS-PS total score will be summarized overall and by cohort (see Section 6.1.2) using descriptive statistics.

Commercially Confidential Information

Commercially Confidential Information

### **8.2.2. TETRAS Upper Limb Subscale Score**

Upper limb tremor is assessed during the following maneuvers: forward outstretched posture, lateral “wing beating” posture, kinetic (finger-chin-finger) testing, Archimedes spirals, handwriting, and dot approximation task. Each side of the body (right and left) is assessed and scored individually for all maneuvers except handwriting. The individual item question scores for each side of the body range from 0 to 4, with higher scores indicating more tremors. Derivation for the upper limb subscale score is described in Section [6.1.8](#).

Assessments will be administered at Screening, Pre-dose, Day 1, Day 7, Day 14, and Day 21. Assessment results (scores) by local and central rater will be analyzed in the same way as described below for central rater score data. Observed values and change from baseline to all subsequent study visits in the upper limb subscale score will be summarized overall, by cohort (see Section [6.1.2](#)), and by study visit using descriptive statistics.

Additionally, tests of hypotheses comparing mean and median TETRAS-PS upper limb subscale scores between baseline and subsequent study visits will be conducted using a 2-sided paired t-test and a Wilcoxon signed rank test, respectively. The null hypothesis is that the change from baseline in TETRAS-PS upper limb subscale score to subsequent visit is 0 with a 2-sided alternative considering a difference in either direction (i.e., change from baseline not equal to 0, representing significant change in tremor).

As a supportive analysis, change from Screening to Baseline and change from Day 14 to Day 21 in each item score and in TETRAS-PS upper limb subscale score will be summarized overall and by cohort (see Section [6.1.2](#)) using descriptive statistics.

Commercially Confidential Information

